In **Aim 1a**, I will compare using Replicating Effective Programs (REP) and Enhanced REP to deliver the Life Goals Collaborative Care: LGCC intervention on program fidelity and participant alcohol, tobacco, and other drug (ATOD) use. LGCC is an EBP developed for psychiatric disorders, which also addresses substance use. ⁶⁰ Similar to MMH, LGCC emphasizes skill building for behavior change to reduce negative outcomes. ⁶¹ LGCC has undergone customization guided by feedback on factors related to implementation in initial clinical trials and additional adaptations to include two conditions of enhanced REP. I will compare these conditions on fidelity and ATOD use. This will provide critical experience investigating implementation strategies to prepare me for applying REP in a novel setting- schools (Aim 3). In **Aim 1b**, Guided by the Costs of Implementing New Strategies (COINS) framework, I will estimate the costs and cost-effectiveness of REP and Enhanced REP on LGCC intervention fidelity and participant ATOD use. **Sample**. Eighty community clinics received standard REP at the start of the study. After 6 months, the non-responsive sites (n=60) were randomized to receive enhanced REP with both external facilitation: EF and internal facilitation: IF (n=30, 600 participants) or EF only (n=30, 600 participants) to facilitate LGCC implementation. **Procedures**. The study incorporated a sequential, multiple assignment, randomized trial design that included implementation and effectiveness components. ⁴³ Data were collected at 6 and 12 months following randomization.

Mid-year progress Aim 1b: I have a manuscript for the ADEPT cost-effectiveness analysis under review.

Aim 1a. Measures. ATOD use. Using items from the National Institute on Drug Abuse's Modified Alcohol, Smoking and Substance Involvement Screening Test⁶³ and the Alcohol Use Disorders Identification Test⁶⁴ we assessed past month marijuana, illegal drug, and tobacco use and binge drinking. We will create a summed

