Aim 1b: Measures. Implementation costs: Implementation costs will be guided by the COINS approach (see Table 7). Implementation costs include indirect costs such as time spent training and supervising, training compensation (e.g., pay during non-work hours), time costs of assisting with intervention delivery, and nonlabor costs such as costs of the curriculum (manual and materials), training time, technical assistance, facilitator time, and travel costs. 13,72 Data analytic approach. We will estimate the costs of each REP condition using data in Table 7, with the base case analysis being the enhanced REP+EF (external facilitation) only. The primary outcome will be change in reported ATOD use during the intervention period. We will use net costs (net increase in costs from the enhanced REP condition with external: EF and internal: IF facilitation compared to EF only) and net effectiveness (net decrease in substance use from the enhanced REP condition with EF and IF compared to EF only) to calculate the incremental cost-effectiveness ratio for behavioral and implementation outcomes: $\frac{\textit{Cost}_{E-\textit{REP}:IF+\textit{EF}} - \textit{Cost}_{E-\textit{REP}:EF}}{\textit{Outcome}_{E-\textit{REP}:EF}}$ —. We will conduct uncertainty analyses to evaluate variability in results from potential bias in parameter estimates (e.g., duration of consultations for facilitation) and use these results to construct confidence intervals around cost and cost-effectiveness estimates as a measure of uncertainty around results.73 We will also conduct sensitivity analyses to characterize how extensive an implementation strategy must be to justify a change in approach from a behavioral (e.g., ATOD use) and economic perspective. We will vary certain assumptions to meet a range of possible scenarios (e.g., extent of facilitation).⁴⁵ These analyses will be essential in informing economic evaluation for the pilot study. **Expected outcome**: We expect patients in the enhanced REP with IF and EF will report a greater reduction in ATOD use relative to dollar spent compared to those in REP with IF.

Mid-Year Progress Aim 2: Since the end of Year 1, I have had two papers related to this research published, one in Prevention Science, and one in the Journal of School Health. I have also submitted a qualitative study related to the project that is currently under review.

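### As written, the Aim 1b confidence intervals reflect possible bias in input parameters and carry no clustered sampling error for the ATOD difference in the ratio's denominator

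*Combined protocol and SAP*

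**What the plan says.** The Combined protocol and SAP, AIM 1 (Sample), describes the data: "the non-responsive sites (n=60) were randomized to receive enhanced REP with both external facilitation: EF and internal facilitation: IF", or EF only, with 30 clinics and 600 patients in each arm. On follow-up it states: "Data were collected at 6 and 12 months following randomization".

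The Aim 1b data analytic approach defines the effect side of the ratio: "The primary outcome will be change in reported ATOD use during the intervention period". Net cost is divided by net effectiveness, comparing EF plus IF with EF only. One sentence then covers interval construction. The uncertainty analyses are to "evaluate variability in results from potential bias in parameter estimates (e.g., duration of consultations for facilitation"), and the team will "use these results to construct confidence intervals around cost and cost-effectiveness estimates". A reference is cited there for the approach.

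A separate sentence follows on sensitivity analyses, in which assumptions such as the extent of facilitation are varied over scenarios. That sentence is not tied to any confidence interval.

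Clustering appears within Aim 1 only in the Aim 1a data analysis, where the growth curve model of ATOD use is to allow for nesting. The level of nesting is not named, and no link from that model to the Aim 1b intervals is stated.

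**The concern.** A confidence interval for a cost-effectiveness ratio should reflect how far the ratio could move if other clinics and patients had been sampled. The only source of variation that Aim 1b names is possible bias in inputs, and its one example is a cost input. Bias in an input is not sampling error. A range obtained by shifting inputs depends on the spans chosen and has no coverage property.

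The denominator is the sensitive part. It is a difference between two groups of 30 clinics, and its uncertainty includes between-clinic variation. If the difference is compatible with zero, the ratio has no finite upper limit. An interval that moves only cost inputs stays finite whatever the data say about the effect.

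Two things raise the stakes. Aim 1b says that these analyses will inform the economic evaluation of the pilot, and the mid-year progress note reports a manuscript on the cost-effectiveness analysis under review.

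**Working it through.** Aim 1b states no power, SD, ICC, cost or interval, so there is no figure of the plan's own to reproduce. The check asks whether the component missing from the written rule is large enough to matter.

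**Inputs from the documents (AIM 1, Sample)**
- Clinics: "the non-responsive sites (n=60) were randomized to receive enhanced REP"; 30 + 30 = 60.
- Patients: 600 + 600 = 1,200.
- Mean cluster size: 600/30 = 20 patients per clinic.

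**Assumptions, not in the documents**
- ICC from 0 to 0.10, with 0.01 to 0.05 as the working range.
- True effect of 0.1, 0.2 or 0.3 SD.
- Net cost fixed at 1 unit, and cost inputs varied by ±20% for comparison.
- No baseline adjustment in the main figures.

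**Step 1. Sampling error of the effect.** Design effect DE = 1 + (20 − 1) × ICC; SE = √(2 × DE/600) in SD units; 95% half-width = 1.96 × SE.

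| ICC | DE | SE (SD) | Half-width (SD) |
|---|---|---|---|
| 0 | 1.00 | 0.058 | 0.113 |
| 0.01 | 1.19 | 0.063 | 0.123 |
| 0.05 | 1.95 | 0.081 | 0.158 |
| 0.10 | 2.90 | 0.098 | 0.193 |

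For a true effect of 0.2 SD, the half-width is 0.123/0.2 = 62% of the effect at ICC 0.01 and 0.158/0.2 = 79% at ICC 0.05.

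**Step 2. What this does to the ratio.** With net cost 1, the ratio is 1/effect. The limits from sampling error are 1/(effect + half-width) and 1/(effect − half-width). The range from cost inputs alone is 0.8/effect to 1.2/effect.

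| True effect (SD) | Ratio | Cost inputs ±20% | Sampling error, ICC 0.01 | Sampling error, ICC 0.05 |
|---|---|---|---|---|
| 0.1 | 10.0 | 8.0 to 12.0 | 4.5 to no finite limit | 3.9 to no finite limit |
| 0.2 | 5.0 | 4.0 to 6.0 | 3.1 to 13.1 | 2.8 to 23.8 |
| 0.3 | 3.3 | 2.7 to 4.0 | 2.4 to 5.7 | 2.2 to 7.0 |

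At 0.1 SD the effect interval is −0.023 to 0.223 (ICC 0.01) or −0.058 to 0.258 (ICC 0.05). It includes zero even at ICC 0 (−0.013 to 0.213).

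**Step 3. Effect of baseline adjustment.** Aim 1a plans to control for baseline. With an assumed baseline correlation of 0.5, the SE is multiplied by √(1 − 0.25) = 0.87. The half-widths become 0.123 × 0.87 = 0.11 and 0.158 × 0.87 = 0.14 SD. In the other direction, the mid-year note for Aim 1a says that missing data are still being addressed, so fewer than 1,200 patients may contribute.

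**The case against.** The best defence is that omission is inferred. The plan does not say that only cost inputs enter the interval: consultation duration is given as an example, and parameter estimates could include the ATOD difference. The cited reference, which is not available here, may describe a method that carries sampling variance. This stands as a reason for caution. It does not repair the text, which names bias as the source of variation and mentions no bootstrap, Fieller, net-benefit or other method that would bring in sampling error.

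A reader might infer that the intervals are simply the ranges from varying assumptions over scenarios. The documents do not support that. Scenario variation belongs to the separate sensitivity sentence, so the plan already distinguishes the two steps.

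A reader might also infer that Aim 1 as a whole could not reveal an ATOD difference near zero. That goes too far. The Aim 1a growth curve model compares the same two arms on ATOD use and allows for nesting, so its standard error could show this. What is missing is a stated route from that model to the Aim 1b interval.

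Finally, it is tempting to prescribe a joint bootstrap of cost and effect by clinic. Aim 1b estimates costs for each condition, and Table 7 lists activities and resource types by phase. Neither shows that costs exist clinic by clinic. Without them there are no cost-effect pairs to resample. This objection stands and shapes the fix.

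**Conclusion.** The point holds in this form: the written rule for the Aim 1b intervals brings in no sampling error or clinic clustering for the ATOD difference. The counts behind it are the documents' own. Under an assumed ICC of 0.01 to 0.05 without baseline adjustment, the missing component is a 95% half-width of about 0.12 to 0.16 SD, which is not negligible for effects of 0.1 to 0.3 SD. An interval built only on input bias could therefore understate the uncertainty and could stay finite where the ratio has no finite upper limit.

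A reader might conclude that the planned intervals are shown to be far too narrow. The documents do not allow that. They give no ICC, effect size, cost or input span, so the comparison in the working rests on assumed values. The conclusion about the written rule does not depend on them.

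This is a correction to a secondary analysis. It changes neither the conduct nor the size of the MI-LEAP pilot.

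**What to change.** State in Aim 1b how the interval is formed, and include the clustered sampling error of the ATOD difference:

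- Either resample clinics within arm, or draw the effect from the Aim 1a estimate and its standard error, after confirming that the model accounts for clustering at clinic level.
- If clinic-level costs exist, resample cost and effect together, so that their correlation is kept. If costs exist only by condition, combine the sampling distribution of the effect with the input uncertainty on the condition-level costs.
- Report incremental cost and incremental effect, with net benefit or an acceptability curve, so that the result remains interpretable when the effect may be zero.
- Label any range that comes only from input bias as a sensitivity range, not a confidence interval.

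If the team already intended parameter estimates to include the ATOD effect with its clustered standard error, a sentence saying so would settle that part.

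The outcome data have been collected, so the cost is modest extra analysis and an update to the reported intervals. The downside is that the intervals will be wider and may look less favourable.

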AIM 2: Evaluate factors associated with the fidelity of a school-based ATOD prevention program (the Michigan Model for Health: MMH) to tailor an implementation strategy.

The objective of Aim 2 is to investigate factors associated with implementation guided by CFIR to better understand implementation in school settings (Figure 1). This will inform Replicating Effective Programs (REP) design for MMH delivery. This research is expected to provide information regarding barriers and facilitators to MMH implementation and foundational knowledge to effectively design implementation strategies. **Overview**. I will use data from an ongoing study (Health Education Experts Study) of high school health teachers and administration to assess factors related to the implementation of an EBP.³⁰ This includes quantitative and qualitative data addressing factors across multiple domains guided by CFIR. **Sample and setting**. Participants are Michigan high school health class teachers, high school administrators, and other key personnel in MMH implementation (e.g., Regional Health Coordinators). We currently have survey (n=20) and interview (n=4) data from participants in Genesee County collected in collaboration with the GISD Regional Health Coordinator. We will recruit additional participants in collaboration with MI DHHS through their network of Regional Health Coordinators. MI DHHS has successfully recruited health teachers and administrators in previous health curricula studies and they are deeply committed to supporting MMH delivery.²⁸ We expect to recruit 200 more teachers for the survey based on response rates from previous MI DHHS surveys. With this

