to implementation.³³ Factors included in this study are informed by previous school-based research and input from community partners at GISD and MI DHHS; this includes constructs related to the intervention (e.g., packaging/manual), context (e.g., implementation climate) and providers (e.g., knowledge and beliefs).³² The implementation outcome is dose delivered: a fidelity dimension. 12 We assess dose delivered by asking about the proportion of the MMH curriculum teachers reported delivering to students, from 0: none to 4: 75% or more. The measure is consistent with dose delivered in a previous study of MMH.²⁸ The semi-structured interviews focus on the intervention, context, and provider characteristics, including barriers and facilitators to MMH delivery. Data Analysis: Quantitative data analysis: We will use multinomial logistic regression models to estimate the probability of an outcome relative to a baseline category for a given set of predictors. 58 We will account for nesting by school as needed; our community partners indicate, however, that many high schools in Michigan are staffed by one certified health teacher. Guided by Hosmer and Lemeshow's approach, 59 we will choose variables for inclusion based on statistical and substantive contributions to the overall model.⁵⁹ In the interest of parsimony and reducing model over fitting, we will use both theoretical considerations and the Wald test to eliminate variables that do not contribute to the model. Qualitative Data analysis: We will analyze

the structured interviews using N-vivo. First, we will mark separate segments responses that represent distinct constructs. Next, we will review data chunks to establish agreement and then assign chunks into meaningful categories guided by CFIR. Next, we will combine categorized data chunks. Finally, we will review data to identify common themes. Results from qualitative data analysis will inform model building and provide context for interpreting and applying quantitative results. **Expected outcomes:** We expect to identify specific factors across CFIR domains that influence dose delivered.³³ For example, we may find that teachers report MMH is not fully meeting students' needs around substance use and that this is associated with less dose delivered. These results will be critical to informing REP for the pilot study (Aim 3).

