Aim 3: MMH REP pilot: building on the skills developed in Aim 1 and Training Goals 1-3, I will conduct a prospective implementation pilot of the MMH in the GISD. REP is well suited for implementing MMH because it includes a curriculum manual and teacher training processes. The overall purpose of this pilot is to assess the appropriateness, feasibility, and acceptability of using REP for MMH, a universal ATOD prevention program. 62 I will create a customized package for delivering MMH using standard and enhanced REP. Informed by data from Aim 1, I will investigate the effectiveness of standard and enhanced REP on implementation and behavioral outcomes. Sample and setting. We will study high schools from Genesee County, MI. Like other communities facing declining populations and economic challenges, the county has had higher unemployment levels compared to state and national averages for over a decade, 66 and youth report higher rates of ATOD use compared to state averages (Table 6). This pilot study will include 8 schools from the Genesee Intermediate School District (GISD), as informed by other implementation pilot studies⁶² and study resource limitations. GISD includes 21 school districts and 25 public high schools. In collaboration with GISD partners, we will identify high schools using MMH that fail to meet MI DHHS standards for implementation (75% or less of the curriculum) to contact regarding participation. We will select schools using data from our MMH implementation study that have comparable student demographics (e.g., % free/reduced lunch). Procedures. We will recruit schools in collaboration with GISD leadership. Identified schools will be randomized to either standard REP or enhanced REP (see Table 3). The standard REP condition will receive a customized MMH manual (adapted from the current manual) based on results from Aim 2 to meet the needs of the context and providers; this may include creating on online manual. Standard REP will also include customized training based on Aim 2 (e.g., adapting content to new substances or substance forms, updated teacher resources) and brief, as needed technical assistance. Enhanced REP will also include internal and external facilitators with specific expertise in health education and implementation with weekly teacher contact to provide specific guidance for overcoming MMH delivery barriers. Enhanced REP will also include additional training and packaging customization (e.g., supplemental ATOD resources). The study team will meet with teachers and parents at participating schools to share study information. Teachers will complete a survey on MMH implementation and using Enhanced REP to deliver MMH post-intervention. We will also conduct qualitative interviews of teachers in participating schools to obtain in-depth information about using MMH delivery with REP. Students receiving the MMH at participating schools will be eligible for student-level surveys. Students will be recruited in participating schools in conjunction with GISD partners. Following parental consent and participant assent, students will complete a self-administered questionnaire through a secure, online survey about ATOD and related behaviors. As MMH is integrated as part of the school curriculum, students will complete the initial survey during their 9th or 10th grade health class prior to MMH delivery and 3 months postdelivery. Students who do not consent will receive an alternate activity. I expect 300 students to participate based on a 60% response rate. 67 Students will receive \$10 for the surveys.

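### The plan randomises 8 schools with no stated ratio or restriction; fixing 4:4 and restricting on one or two school variables would cut chance imbalance

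*Combined protocol and SAP*

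**What the plan says.** All of this is in APPROACH, Aim 3, unless another place is named.

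- **Size (Sample and setting):** "This pilot study will include 8 schools from the Genesee Intermediate School District (GISD". The number rests on other pilots and on resources.
- **Pool:** "GISD includes 21 school districts and 25 public high schools". The number eligible is not given.
- **Entry:** "we will identify high schools using MMH that fail to meet MI DHHS standards for implementation (75% or less of the curriculum".
- **Selection:** "We will select schools using data from our MMH implementation study that have comparable student demographics (e.g., % free/reduced lunch".
- **Allocation (Procedures):** "Identified schools will be randomized to either standard REP or enhanced REP (see Table 3". Nothing elsewhere in the document adds a ratio, sequence method, stratification, matching or constraint.
- **Student baseline (Procedures):** "students will complete the initial survey during their 9th or 10th grade health class prior to MMH delivery and 3 months postdelivery". Whether this comes before or after randomisation is not stated.
- **Analysis (Aim 3a, Data analytic approach):** the models for substance use and its consequences adjust for demographics and baseline functioning and allow for clustering by school. For adherence, the plan says only that the composite score will be used. The cost-effectiveness ratio in Aim 3b is built from differences between conditions, with no adjustment stated.

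**The concern.** With 8 units, the allocation method is one of the main design decisions. Adherence, student substance use and the cost-effectiveness ratio are all compared between two small groups of schools. If one arm happens to start with schools that already deliver more of the curriculum, or serve a different student population, that difference goes straight into the estimated effect.

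The pilot says it aims to report effect estimates, their variance and their direction, and to use the variance estimates to size a larger study. Chance imbalance between arms distorts effect size and direction. The plan already intends to use school data to choose schools, but gives no role to those data in deciding which school goes to which arm.

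**Working it through.** The plan gives no allocation ratio, power or intraclass correlation for Aim 3, so there is no stated figure to reproduce. The only input from the document is 8 schools.

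**1. Arm sizes if each school were allocated independently (an assumption; the plan does not say so).** Binomial(8, 0.5):

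- P(4:4) = C(8,4)/2^8 = 70/256 = 27.3%, so P(unequal) = 72.7%.
- P(6:2 or worse) = 2 × (1 + 8 + 28)/256 = 28.9%.

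Variance of a school-level contrast relative to 4:4 is (1/a + 1/b)/(1/4 + 1/4):

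- 5:3 gives 1.07
- 6:2 gives 1.33
- 7:1 gives 2.29

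**2. Imbalance under unrestricted 4:4.** Take one school covariate, normal, in units of its between-school SD. The difference in arm means has SD √(1/4 + 1/4) = 0.707.

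- P(|difference| > 0.5) = 2 × [1 − Φ(0.5/0.707)] = 48%.
- P(|difference| > 1) = 2 × [1 − Φ(1/0.707)] = 16%.
- For two independent covariates, P(either > 0.5) = 1 − (1 − 0.4795)² = 73%, and P(either > 1) = 1 − (1 − 0.1573)² = 29%.

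**3. Restricted allocation.** There are 70 possible 4:4 allocations. Rank them by the summed squared arm differences on the balancing variables, keep the best k, and draw one at random. The figures for independent allocation and for best 40 and best 18 are simulated with independent normal covariates (at least 20,000 draws; the 8:0 split is excluded under independent allocation). Each allocation and its mirror image are both kept, so the smallest two-sided permutation p is 2/k.

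| Scheme | One variable: >0.5 SD | One variable: >1 SD | Two variables: any >0.5 SD | Two variables: any >1 SD | Smallest p |
|---|---|---|---|---|---|
| Independent allocation | 51% | 19% | 76% | 34% | – |
| 4:4, all 70 | 48% | 16% | 73% | 29% | 2/70 = 0.029 |
| 4:4, best 40 | 15% | 0.1% | 53% | 3% | 2/40 = 0.05 |
| 4:4, best 18 | 0.3% | 0% | 16% | 0% | 2/18 = 0.11 |

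If the two variables are first scaled by the SD seen in the 8 schools, as would happen in practice, the 3% becomes about 5%.

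**4. Limits of the method.** With three variables and the best 40 kept, P(any > 0.5 SD) falls only from 86% to 75%, although P(any > 1 SD) falls from 40% to 11%. For a factor left out of the allocation but correlated 0.3, 0.5 or 0.7 with a single balanced one, the root-mean-square imbalance falls from about 0.71 SD to only 0.68, 0.62 or 0.52 SD, even with the best 18 kept.

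**5. What selecting comparable schools could do.** Suppose the 8 most similar of m eligible schools are chosen on one covariate, then allocated by unrestricted 4:4. P(> 0.5 population SD) on that covariate is 49% for m = 8, 16% for m = 12, 4% for m = 16 and below 0.1% for m = 25. The document does not give m, so this range is an assumption.

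**The case against.** The strongest case against has five parts.

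- **The plan does not say simple randomisation.** A reader might infer coin-flip allocation from the one sentence. The document is silent, and 4:4 is compatible with it. The 73%, 29% and 33% figures therefore describe what the text permits, not what it states, and the likeliest unequal split, 5:3, costs only 7% in variance. This stands. The imbalance point does not depend on it, because the 48% already assumes 4:4.
- **Safeguards exist.** Selection on comparable demographics could remove most of the demographic imbalance if many schools are eligible (step 5), and the entry criterion narrows prior delivery. This stands in part. The number eligible is unknown, selection is on demographics, and the criterion is only a ceiling, so delivery can vary widely below it.
- **The analysis adjusts.** It would be too strong to say that imbalance cannot be handled at all: substance use has an individual baseline from an expected 300 students. But no adjustment is stated for adherence or the cost-effectiveness ratio. Eight schools leave 8 − 2 = 6 degrees of freedom after the two arm means, and each school-level covariate takes another.
- **Restriction does not remove imbalance in general.** A reader might expect it to. With three variables and a loose restriction the gain is modest (step 4), and factors not used gain little. This stands, and is why one or two variables are proposed.
- **The data may not be in hand.** A reader might infer that delivery is already recorded for every school. The document shows only "We currently have survey (n=20) and interview (n=4) data from participants in Genesee County" (Aim 2, Sample and setting), with delivery self-reported by teachers on a coarse 0 to 4 scale and further recruitment planned. Availability has to be confirmed school by school.

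**Conclusion.** The concern holds in this form: the allocation of 8 schools is given without a ratio or restriction, and a restricted 4:4 draw is a better and inexpensive method even if 4:4 was always intended. Unrestricted 4:4 leaves a 48% chance of a difference above 0.5 between-school SD on a given school covariate, and 16% above 1 SD. These figures assume unselected schools and normal, independent values. They are upper-end figures for demographics if selection works well, and less affected by selection for prior delivery.

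The documents do not support saying that the plan chose simple randomisation, or that restriction would balance everything. Student substance use would gain little unless its baseline is collected before randomisation. The pilot's main purpose is appropriateness, feasibility and acceptability, which limits the harm. The point is still worth acting on, because it cannot be repaired after allocation.

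**What to change.** In Aim 3, Procedures:

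1. State a 4:4 allocation.
2. Draw the allocation at random from the better-balanced of the 70 possible 4:4 allocations. Balance on one or two school-level variables obtained before randomisation: baseline share of MMH delivered, from the teacher survey, and percentage on free or reduced-price lunch.
3. State in advance the balance score and how many allocations are kept. Keeping 40 leaves a two-sided permutation p of 0.05 reachable. Keeping 18 balances two variables much better (16% against 53% for any difference above 0.5 SD), with a smallest p of about 0.11. That matters little here, because the plan puts estimation ahead of significance and has no permutation test.
4. In Aims 3a and 3b, say how the balancing variables enter the comparisons of adherence, substance use and cost-effectiveness.
5. State whether the student baseline survey comes before or after randomisation.

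Cost: a few lines of text, a short script, confirmation that the balancing data are held for each recruited school, and an analysis that respects the restriction.
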